5.5.2 Screen Failures

Enrolled subjects failing to meet inclusion / exclusion criteria at the time of index procedure will not be treated with the EndoRotor® device or the control device and; therefore, are classified as screen failures. Any baseline study data captured in the CRFs will be collected. Only subjects in whom the EndoRotor® catheter or ablative therapy catheter enters the esophagus will be followed and study data analyzed [per protocol set (PPS)].

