7.0 STATISTICAL METHODS

7.1 General Principles

By-subject listings will be created for each CRF module. Summary tables for continuous variables will contain the following statistics: N, mean, median, standard deviation, minimum, maximum, and 95% confidence interval (CI) as appropriate. Summary tables for categorical variables will include N, percentage, and 95% CIs on the percentage. CIs for proportions will be calculated using the Clopper- Pearson exact method. Graphical techniques will be used when such methods are appropriate and informative. Tables will separate data by treatment arm.

Transformations of the data may be explored if warranted by the distribution of the data. Analyses resulting from transformations applied after the data are unmasked will be considered to be exploratory.

Unless otherwise specified, all analyses will be 2-sided at the 0.05 level of significance. All analyses will be performed using SAS® (Version 9.4) and graphs using R, version 3.3.1 or later, or using SAS®.

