7.2 Analysis Populations

The safety analysis population is defined as all subjects who are treated with either EndoRotor® or continued ablative therapy. Subjects will be analyzed as treated.

The primary effectiveness analysis population is intent to treat (ITT), defined as all subjects who are randomized. Subjects will be analyzed as randomized. Missing primary and secondary endpoint data will be imputed.

A supportive effectiveness analysis population is Per Protocol (PP). This population is a subset of ITT and requires that subjects be treated with either EndoRotor® or continued ablative therapy, meet all inclusion/exclusion criteria, and are evaluated for effectiveness at no fewer than two post-treatment visits 3 months apart. Subjects will be analyzed as treated. Missing data will not be imputed.

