7.3 Sample Size

Assuming a response rate for Barrett's esophagus with EndoRotor® ablative therapy of 80%, and for cryoablation of 50%, the study will have over 95% power to demonstrate non-inferiority (NI), given a NI delta of 10%, of EndoRotor® to cryoablation and will have 91.6% power to demonstrate superiority of EndoRotor® over continued ablative therapy using a sample size of 110 evaluable subjects, 55 in each treatment group.

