7.4 Statistical Analysis

The Primary effectiveness endpoint will be compared across treatment arms using a logistic regression, where the predictor variable is treatment arm with EndoRotor® coded 1 vs 0 for cryotherapy or ablative therapy (i.e., control). Covariates included in the model will be: subject's age, dysplasia (low-grade or high-grade), length of Barrett's lesion in cm, and duration of disease (months). The lower boundary of the predicted proportion

difference will be used to compare the two arms for the non-inferiority test and for the subsequent superiority test. In the event that missing data are present in the ITT analysis population, then multiple imputation will be performed with SAS procedures MIIMPUTE and MIANALYZE, as described in section 7.5.

The secondary endpoint, percentage reduction, will be compared using a Wilcoxon rank-sum test. In the event of missing data, The ITT analysis will be performed with data imputed by multiple imputation.

In the event of missing data, sensitivity analyses will be performed for the ITT analysis population using best case and worst case analyses as described below. Discrepant findings will be followed by tipping point analyses.

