7.5 Missing Data

1. If there are missing primary endpoint data, then ten imputations of missing binary primary endpoint will be produced using SAS PROC MI using the Markov chain Monte Carlo algorithm. The seed used to begin random number generation will be 20170623. The following variables will be used as predictors: site, subject's age, dysplasia (low-grade or high-grade), length of Barrett's lesion in cm, and duration of disease (months). Analysis with SAS PROC MIANALYZE will follow.
2. For the secondary endpoint, percentage reduction, ten imputations will be produced for the randomized cohort using SAS PROC MI. The seed used to begin random number generation will be 20170623. The Markov chain Monte Carlo method will be used to compute full imputations using the following variables: site, subject's age, dysplasia (low-grade or high-grade), length of Barrett's lesion in cm, and duration of disease (months). Analysis with SAS PROC MIANALYZE will follow.

The following secondary analyses will be performed to assess the sensitivity of the results to missing data for the primary effectiveness endpoint.

- The best-case scenario will assume success for all missing data treated with EndoRotor and failure for all missing data treated with control.
- The worst-case scenario will assume failure for all missing data treated with EndoRotor and success for all missing data treated with control.
- If the best and worst case analyses lead to different statistical conclusions, then a tipping point analysis will report the proportion of successes or failures for each arm at point the statistical conclusion would change.

A similar approach will be used for the continuous percentage secondary endpoint. Best case will assume 100% removal for EndoRotor® and 0% for control; worst case will assume 0% removal for EndoRotor® and 100% for control; If the results differ using the two imputation rules, then the imputed values will be incremented on 1% values until the point where the conclusion changes is identified.

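### Section 7.5 words the best- and worst-case rules by treatment received, in conflict with the as-randomized ITT population they serve; separately, section 7.2 counts per-protocol crossovers in the arm received

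*Combined protocol and SAP*

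**What the plan says.** Section 7.2 makes ITT the primary effectiveness population, "defined as all subjects who are randomized. Subjects will be analyzed as randomized". Section 7.4 attaches the bounds to that population: "sensitivity analyses will be performed for the ITT analysis population using best case and worst case analyses". Section 7.5 then gives the adverse rule, "The worst-case scenario will assume failure for all missing data treated with EndoRotor and success for all missing data treated with control", and a mirror-image best-case rule with the same wording. A tipping-point analysis follows only if the two cases lead to different statistical conclusions.

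The plan allows for subjects who are randomized and not treated. Randomization takes place within two weeks of the procedure (section 5.2). Subjects found ineligible at the index procedure are not treated (section 5.5.2), and consent can be withdrawn before catheter insertion (section 4.14). Section 5.5.2 adds: "Only subjects in whom the EndoRotor® catheter or ablative therapy catheter enters the esophagus will be followed".

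For the per-protocol (PP) set, section 7.2 asks for treatment with either therapy, not with the assigned one, and says: "Subjects will be analyzed as treated. Missing data will not be imputed". Section 7.2 calls PP supportive, but the Primary Analysis row of the Protocol Summary names per protocol.

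**The concern.** A bound meant for an ITT analysis should give a value to every randomized subject without an outcome, by randomized arm. Rules keyed to treatment received do this only if everyone is treated as assigned. A subject who is randomized and never treated is not followed, so the endpoint is missing, yet the subject was treated with neither device. A crossover with missing data would receive the value meant for the other arm.

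The best-case, worst-case and tipping-point analyses are the sensitivity analyses that the plan names for missing data. If untreated subjects fall outside the rules, the two cases move closer together, and the tipping-point step may not be triggered. A rule open to two readings can also end up being settled once the data are known.

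The PP rule is a separate matter and does not touch the bounds. A subject randomized to one therapy and given the other stays in PP and counts in the arm received. For such subjects that is an as-treated comparison.

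**Working it through.** **Inputs from the documents.** Design rates of 80% and 50% with 55 evaluable per arm (section 7.3); non-inferiority margin 10 points (sections 7.3 and 7.6); two-sided 0.05 (section 7.1); 120 enrolled to reach 110 evaluable, with 10 allowed for loss to follow-up (section 4.5).

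**Assumptions.** 60 randomized per arm, 5 missing per arm, of whom *u* were never treated. The documents give no value for *u*, so 0 to 5 is considered. *Literal* means that untreated subjects are left out of numerator and denominator; *fixed* means that all 5 receive the bound by randomized arm. Intervals are unadjusted: d ± 1.96 × √[p₁(1−p₁)/n₁ + p₂(1−p₂)/n₂]. The plan's own analysis is a covariate-adjusted logistic model, so these figures are illustrative.

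**Plan's own figure.** Superiority power with pooled variance under the null: (0.30 − 1.96 × 0.0910)/0.0863 = 1.41, so power is 92.1%, close to the stated 91.6%. The present point does not affect it.

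**Illustration, 40/55 versus 28/55 observed, u = 5.**
- Literal, both cases: 72.7% − 50.9% = +21.8 points, SE 9.03, 95% CI 4.1 to 39.5, p = 0.016. The two cases coincide, so no tipping-point analysis is triggered.
- Fixed, worst case: 40/60 − 33/60 = 66.7% − 55.0% = +11.7, SE 8.85, CI −5.7 to 29.0, p = 0.19.
- Fixed, best case: 45/60 − 28/60 = +28.3.

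The superiority conclusion is lost in the fixed worst case. The lower limit of −5.7 is still inside the −10 margin, so non-inferiority is kept.

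**Dependence on u.** Worst-case lower 95% limits in points, with untreated subjects left out; u = 0 is identical to the fixed rule:

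| Observed | u = 0 (fixed) | u = 1 | u = 3 | u = 4 | u = 5 |
|---|---|---|---|---|---|
| 80% vs 50% of 55 | 2.3 | 4.3 | 8.5 | 10.7 | 13.1 |
| 40/55 vs 28/55 | −5.7 | −3.9 | −0.04 | 2.0 | 4.1 |
| 40/55 vs 30/55 | −8.9 | −7.2 | −3.5 | −1.5 | 0.5 |
| 36/55 vs 30/55 | −15.9 | −14.3 | −10.9 | −9.2 | −7.3 |

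At the design rates the distance between worst and best case falls from 16.7 points (19.2 to 35.8) at u = 0 to 13.5 at u = 1 and to zero at u = 5, but every lower limit stays above zero. In the second row the superiority conclusion differs from the fixed rule only when 4 or 5 of the missing subjects per arm are untreated, and in the third row only when all 5 are. In the last row the non-inferiority conclusion differs only at u = 4 or 5.

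**PP crossovers, assumed example.** Start at 80% versus 50% of 55 (44 and 27.5 expected responders). Let 5 EndoRotor-arm subjects with 20% response (1 responder) receive ablation.
- As treated: 43/50 − 28.5/60 = 86.0% − 47.5% = +38.5.
- Crossovers excluded: 86.0% − 50.0% = +36.0.
- As randomized: +30.0.

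**The case against.** A reader might infer that the plan denies untreated subjects a value and that its bounds are therefore too narrow. The documents do not support that as a statement of fact. Section 7.4 places the analyses in ITT, and section 7.2 says that missing ITT endpoint data will be imputed. Section 7.5 refers to all missing data, reports the tipping point for each arm, and words the secondary-endpoint rule by device name without *treated with*. Section 7.6 speaks of subjects treated with control and then defines the proportion by control arm. Taken together, these favour reading the phrase as shorthand for arm. Nothing says that untreated subjects leave the denominator. This part of the objection stands, and it reduces the point to a conflict in wording.

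It does not remove the conflict. Section 7.2 uses *treated with* for treatment received when it defines the safety and PP sets, and it sets as treated against as randomized. A programmer could defend either reading.

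The size is also open to challenge, fairly. Section 4.5 describes the allowance of 10 as loss to follow-up, not as non-treatment. Section 4.9 places enrollment at catheter insertion, whereas section 5.5.3 has randomization after enrollment, so it is unclear how many untreated randomized subjects could arise. Nor do the documents say that non-treatment would depend on the arm.

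On PP, the plan provides for no crossover: section 4.10 bars other treatments and section 5.7.1 repeats treatment within arm. The five switched subjects are an assumption. The as-treated rule itself, however, is explicit.

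**Conclusion.** The point holds as a conflict between the wording of section 7.5 and the ITT population of sections 7.2 and 7.4. It is not shown that the bounds are too narrow; that follows only if the wording is read literally and some randomized subjects go untreated.

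Under that reading, with 5 untreated per arm and none missing otherwise, a worst case of +11.7 points would be reported as +21.8, enough to hide a loss of superiority in the example chosen. With one untreated subject per arm no worst-case conclusion changes in any scenario shown, and at 80% versus 50% none changes for any number from 0 to 5. The exposure is confined to smaller effects with most of the missing subjects untreated.

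The PP point needs no interpretation: for crossovers the set as defined is an as-treated comparison. In the assumed example the rule adds 2.5 points over exclusion (38.5 − 36.0). How much this matters depends on whether PP is supportive, as in section 7.2, or primary, as in the Protocol Summary.

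**What to change.** In both primary-endpoint bullets of section 7.5, replace *treated with* by *randomized to*. State that every ITT subject without an observed endpoint, treated or not, receives the best- or worst-case value by randomized arm, and that the same holds for the secondary endpoint.

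In section 7.2, limit PP to subjects who received their randomized arm, and keep as-treated analysis for safety only. Reconcile the Protocol Summary, which names per protocol as the primary analysis, with section 7.2, which names ITT.

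The cost is wording. The worst case may be less favourable, and PP may lose a few crossovers. Excluding them removes only part of the selection bias: in the assumed example the difference moves from +38.5 to +36.0 against +30.0 as randomized, so 6.0 of the 8.5 excess points remain. If the sponsor already meant assignment by arm, the change to section 7.5 alters no result.

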7.6 Effectiveness Hypotheses

Primary Endpoint Hypothesis 1 (non-inferiority): It is hypothesized that EndoRotor® will not have fewer subjects with complete removal than those treated with control.

$$\begin{array}{ll} \text{Null Hypothesis:} & nE - \delta \leq nC \\ \text{Alternate Hypothesis:} & nE - \delta > nC \end{array}$$

Where nE =Proportion with successful treatment in EndoRotor® arm; nC = proportion with successful treatment in the control arm and δ is a non-inferiority margin of 10% (which is subtracted from nE).

Primary Endpoint Hypothesis 2 (superiority): The proportion of subjects with successful eradication areas of Barrett's metaplasia will be greater for those treated with EndoRotor® than for those treated with control.

$$\begin{aligned} \text{Null Hypothesis: } & nE \leq nC \\ \text{Alternate Hypothesis: } & nE > nC \end{aligned}$$

Where nE =Proportion with successful treatment in EndoRotor® arm; nC = proportion with successful treatment in the control arm.

Secondary Endpoint Hypothesis: The percentage tissue removal of Barrett's metaplasia will be greater for those treated with EndoRotor® than for those treated with control.

$$\begin{aligned} \text{Null Hypothesis: } & \mu E \leq \mu C \\ \text{Alternate Hypothesis: } & \mu E > \mu C \end{aligned}$$

Where μE =mean % tissue removal for EndoRotor® arm; μC = mean % tissue removal for control arm.

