7.8 Statistical Analysis of Primary and Secondary Effectiveness Endpoints

In testing for non-inferiority of the primary effectiveness, a two-tailed 95% confidence interval (CI) for the difference in two rates will be used to examine the location of the lower boundary of the CI relative to the 10% NI delta. An NI delta of 10% is judged to be clinically acceptable for this indication. Further, given an expected 30% advantage of the test device over the active control (80% vs 50%), by setting the non-inferiority margin at 10%, we are retaining 67% of the active treatment advantage as opposed to a using a

more standard value of 50% (Non-Inferiority Clinical Trials to Establish Effectiveness Guidance for Industry, U.S. Department of Health and Human Services Food and Drug Administration Center for Drug Evaluation and Research (CDER) Center for Biologics Evaluation and Research (CBER) November 2016 Clinical/Medical).

In testing for superiority of the primary effectiveness endpoint, the same logistic regression model, used to test for NI will be evaluated. Alpha of 0.05 will be used to test for significance.

The secondary effectiveness endpoint will be tested with a Wilcoxon rank-sum test. An alpha of 0.05 will be used to test for significance.

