7.8.3 Multiplicity

In the event that the primary effectiveness test of non-inferiority fails to reach significance, further endpoint testing will cease. If the test of non-inferiority is successful, then testing for superiority will proceed. If superiority is demonstrated for the primary effectiveness endpoint, then the secondary endpoint will be tested.

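### The non-inferiority hypothesis carries the margin with the wrong sign: as printed, the gatekeeping test requires EndoRotor to beat control by more than 10 points and has about 64% power, against a stated power of over 95%

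*Combined protocol and SAP*

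**What the plan says.** Section 7.6 gives the first primary hypothesis as non-inferiority and introduces it in words as EndoRotor not having fewer complete removals than control. It then prints the null as nE − δ ≤ nC and the alternative as nE − δ > nC, where "δ is a non-inferiority margin of 10% (which is subtracted from nE".

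Four other sections bear on the same test:

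- **Section 7.3** plans on 80% response with EndoRotor and 50% with control, "using a sample size of 110 evaluable subjects, 55 in each treatment group", and states that "the study will have over 95% power to demonstrate non-inferiority (NI), given a NI delta of 10" percent. It gives 91.6% power for superiority. Section 4.7 gives 90% for superiority and repeats the over-95% figure for non-inferiority.
- **Section 7.4** says the lower boundary of the predicted difference serves both tests, but names no threshold.
- **Section 7.8** says that "a two-tailed 95% confidence interval (CI) for the difference in two rates will be used to examine the location of the lower boundary" relative to the 10% delta, without a sign. It supports the margin by saying that "by setting the non-inferiority margin at 10%, we are retaining 67% of the active treatment advantage".
- **Section 7.8.3** makes this test the gate: "In the event that the primary effectiveness test of non-inferiority fails to reach significance, further endpoint testing will cease". Superiority comes second and the secondary endpoint third.

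**The concern.** Moving δ to the other side turns the printed alternative into nE − nC > +0.10. That is a demand for superiority by more than 10 points, under a non-inferiority label. The null line, the alternative line and the verbal explanation all agree, so this is not a dropped symbol or a fault in the text extraction.

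The printed test also makes the sequence illogical. Step 1 becomes stricter than step 2: any result that passes the gate has already shown superiority, and the superiority test adds nothing. If Section 7.6 is followed, power to claim superiority or reach the secondary endpoint is set by the gate and not by Section 7.3. If the direction is instead settled at analysis, the threshold for the primary claim of a pivotal trial moves by 20 points once data exist.

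The margin rationale has a related fault. The 67% is (30 − 10)/30, taken from the expected gap between EndoRotor and control. A preserved fraction describes how much of the active control's own effect over no treatment is kept, and the plan gives no estimate of that effect.

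**Working it through.** **Inputs.** Response rates are 0.80 and 0.50, with 55 evaluable subjects per arm (Section 7.3). The decision uses the lower limit of a two-sided 95% interval for the difference, so the critical value is 1.96 (Section 7.8). The margin is 0.10 (Sections 7.3, 7.6 and 7.8).

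**Standard error.** SE = √[(0.80 × 0.20 + 0.50 × 0.50)/55] = √(0.41/55) = 0.0863.

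**Power.** The probability that the lower limit exceeds a threshold t is about Φ[(0.30 − t)/SE − 1.96].

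1. *The plan's non-inferiority figure.* With t = −0.10: 0.40/0.0863 − 1.96 = 2.67, giving 99.6%. This agrees with the stated over 95%.
2. *The plan's superiority figure.* With t = 0: 0.30/0.0863 − 1.96 = 1.51, giving 93.5%. With a pooled variance the result is 92.1%, close to the stated 91.6%.
3. *The hypothesis as printed.* With t = +0.10: 0.20/0.0863 − 1.96 = 0.36, giving 63.9%.

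**Exact check.** Summing binomial probabilities over all 56 × 56 outcomes gives:

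| Lower 95% limit above | Wald | Newcombe |
|---|---|---|
| −10 points (ordinary non-inferiority) | 99.5% | 99.5% |
| 0 (superiority) | 93.0% | 92.6% |
| +10 points (Section 7.6 as printed) | 64.0% | 60.2% |

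Other settings do not bring the printed test to 95%. By the normal approximation, a one-sided 0.05 level gives 74.9%, and 60 per arm gives 67.7%.

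**Sample size the printed test would need.** For 95% power: (1.96 + 1.645)² × 0.41/0.20² = 133.2, so 134 per arm.

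**Observed difference needed to pass.** At the planning variance, the printed gate needs more than 0.10 + 1.96 × 0.0863 = 0.269, or about 27 points. Plain superiority needs 1.96 × 0.0863 = 0.169, or about 17 points.

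**Other true rates** (55 per arm, exact, Wald limits):

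| True rates, EndoRotor vs control | Printed gate (+10) | Superiority (0) | Ordinary non-inferiority (−10) |
|---|---|---|---|
| 70% vs 50% | 20% | 60% | 90% |
| 60% vs 50% | 2.7% | 18% | 58% |
| 50% vs 50% | about 0.1% | 2.4% | 19.5% |

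**The case against.** The strongest reply is that no statistician would run the test as printed. The label, the introductory sentence in Section 7.6, the power in Section 7.3 and the order of tests in Section 7.8.3 all point to −10 points. A delta described as clinically acceptable also reads naturally as a tolerated deficit. On this view the stated power is right, and 64% is a hypothetical figure.

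Part of this stands. The over-95% figure is not an arithmetic error: it is correct for ordinary non-inferiority, and the defect is that Sections 7.3 and 7.6 describe different tests. The loss of power occurs only if Section 7.6 is applied literally. However, no section writes the threshold as −10 points, and the only signed criterion in the document is the wrong one. A confirmatory rule should not depend on readers inferring its direction.

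Two narrower points also stand. First, 64% belongs to 55 complete subjects per arm and is not a strict ceiling. With 60 complete subjects per arm, the exact figures are 67.9% (Wald) and 64.5% (Newcombe). Second, the 67% sentence is a separate matter from the sign. Correcting one does not correct the other, and recomputing the fraction would need evidence that the plan does not contain.

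**Conclusion.** The concern holds, and the text must be corrected before the data are unmasked. Read literally, the gate has 60% to 64% power at the planning rates with 55 per arm, against the stated over 95%. Power to claim superiority falls from the stated 91.6% to the same level. Only a threshold of −10 points reproduces the plan's own non-inferiority power, so the intended direction is not in real doubt.

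The figures assume the planned rates, complete data and unadjusted proportions. The covariate-adjusted logistic model and multiple imputation in Sections 7.4 and 7.5 were not simulated and could shift the figures slightly. The contradiction between sections does not depend on any of these assumptions.

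The 67% figure does not support the margin. The separate statement that 10% is clinically acceptable is unaffected.

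**What to change.** - **Section 7.6:** write H0: nE − nC ≤ −0.10 and H1: nE − nC > −0.10 (equivalently nE + δ > nC). Delete the parenthetical remark about subtracting the margin from nE.
- **Section 7.8:** state that non-inferiority is shown if the lower limit of the two-sided 95% interval for nE − nC lies above −10 points, and superiority if it lies above 0. Refer to the same rule in Section 7.4.
- **Section 7.8, margin rationale:** delete the sentence on retaining 67%. If a preserved fraction is wanted, derive it from the control's effect over no treatment.

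The cost is the wording of one hypothesis pair, one decision rule and one rationale sentence. Sample size, data collection and the stated powers need no change. Deriving a new preserved fraction is the only option that needs work outside the plan, and deleting the sentence avoids it.
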